In order to lay the groundwork for a future Merit Review proposal investigating the utility of spatial cognitive training in visual rehabilitation, the currently proposed SPiRE project seeks to establish the feasibility of such training in visually impaired participants over a telehealth interface, to obtain data on the effect size of the training relative to a control intervention to provide a basis for sample size estimation in a larger clinical trial, and to examine the relevant neural mechanisms so as to suggest possible synergistic interventions that would enhance the effects of spatial cognitive training. Importantly, the proposed work will examine the real-world generalizability of the training effects using physical walking spaces to assure relevance to rehabilitation.

Research Design and Methods

PARTICIPANTS

We will recruit 60 blind participants, randomized by our CVNR statistician into two groups. One group will undergo the experimental intervention (spatial cognitive training) and the other will undergo a control intervention involving letter-number matching. The participants will include women and minorities in proportion to the demographics of the veteran population attending the Atlanta VA. Working with our statistician, we calculated that this sample size has a power of 0.81 to detect an effect size of 0.9 with $\alpha=0.05$ and $\beta=0.19$. The randomization process should result in a balance between the intervention and control groups with respect to a range of variables, including age, sex, age of onset of visual loss, duration of visual loss and of loss of light perception, and comorbid conditions; any residual differences will be accounted for as covariates in statistical analyses.

Since the participants are blind or have low vision, they will need transportation to the CVNR, which will be provided via a contractual arrangement in place with the CVNR. Subjects will be compensated for their time at a flat rate of \$150 for participation in all sessions of the study. If they drop out or are otherwise unable to complete the study, compensation will be prorated for the number of sessions they participate in.

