Specific Aim I will test the hypothesis that spatial cognitive training of blind veterans on a spatial imagery task leads to improvements in **(a)** performance on the trained spatial imagery task and **(b)** real-world navigational ability, relative to a control intervention. If the hypothesis is supported, this would be a simple method of spatial cognitive training with real-world benefits that could eventually be administered via telemedicine. **Specific Aim II** will use functional magnetic resonance imaging (fMRI) to assess the neural changes associated with spatial cognitive training. The hypothesis is that those in the spatial cognitive training group will show enhanced activation in brain regions mediating spatial processing, such as the hippocampus and parietal cortex, as well as more differentiated neural representations of imagined paths. The benefit of pinpointing the neural loci of change is the identification of potential targets for application of converging rehabilitation approaches, e.g. transcranial magnetic or electrical stimulation over parietal regions; enhancing hippocampal neurogenesis through aerobic exercise. If the present proposal is successful, subsequent research will be needed to determine how best to incorporate such training into programs that complement current O&M training.

ANALYSES

In **Specific Aim I**, each behavioral measure will be subjected to a repeated-measures ANOVA with a between-subjects factor of group (experimental, control) and a within-subjects factor of session (pre-training, post-training); the null hypothesis will be rejected in case the interaction is significant at $\alpha=0.05$. If the interaction is non-significant, the Bayes factor will be calculated to ascertain whether this (less likely) supports the null hypothesis or (more likely) reflects insufficient power (Dienes, 2014); in the latter case, the data can be used to estimate the sample size for a subsequent study. In **Specific Aim II**, the imaging measures acquired (except

for DTI) will be subjected to similar two-factor ANOVAs as in Aim I, and statistical interpretations will follow similar lines.

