We predict that spatial cognitive training, but not the control intervention, will lead to improvements in performance on the spatial imagery task, its analog in the MSL, and the various functional neuroimaging measures. There may be transfer of spatial learning to the spatial memory task, but we do not expect transfer to the verbal memory and working memory measures, indicating the spatial specificity of training. We hypothesize that spatial cognitive training, but not training on the control intervention, will lead to increases in activation in cortex along the IPS and in the FEFs as well as in the hippocampus, increased strength of connectivity between these regions in the task and resting states, and also to more differentiated representations between different paths (i.e. their representations will show higher dissimilarity). The behavioral and neuroimaging measures obtained at baseline, including DTI measures of structural connectivity between the activated brain regions, will be tested as regressors to establish whether they predict changes in the repeated measures. This will be useful to examine the impact of individual differences in pre-training spatial and verbal abilities on the effects of training, and in the design of further studies aimed at targeting interventions tuned to individual performance in specific domains.

TIMELINE

First 2 months: Set up tasks and initiate recruitment

Next 20 months: Test and train 2 subjects per month, one in each group

Last 2 months: Analyze data and prepare publications

FUTURE DIRECTIONS

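### The stated power of 0.81 does not follow from 60 participants (60 gives 0.93), and the timeline tests only 40

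*Combined protocol and SAP*

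**What the plan says.** The Participants section (Research Design and Methods) gives one study size: "We will recruit 60 blind participants, randomized by our CVNR statistician into two groups". Three sentences later it states that "we calculated that this sample size has a power of 0.81 to detect an effect size of 0.9", "with $\alpha=0.05$ and $\beta=0.19". It gives no sidedness, does not name the test behind the calculation, does not say what 0.9 is standardised by, and allows for no dropout. Dropout appears there only in connection with prorated payment.

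The Analyses section bases the Aim I decision on the group-by-session term of a two-group, two-session repeated-measures ANOVA: "the null hypothesis will be rejected in case the interaction is significant at $\alpha=0.05".

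The Timeline section has three lines: two months of set-up, then "Next 20 months: Test and train 2 subjects per month, one in each group", then "Last 2 months: Analyze data and prepare publications".

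**The concern.** Sample size, power and schedule should describe the same trial, and here they do not. The only size to which the power statement can refer is 60, yet 0.81 is well below what 60 participants give for an effect of 0.9. The schedule stops at 40, which is also roughly the size at which 0.81 is correct.

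Three things depend on this:

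- **Feasibility.** The project is meant to show that the training can be delivered and to inform the size of a larger trial. A schedule that covers two thirds of the stated enrolment works against that aim. The protocol also opens recruitment to the community because the local veteran population has not supplied enough participants, so a shortfall is a realistic prospect.
- **Reading a null result.** The Analyses section expects a non-significant interaction to reflect low power more probably than a true null. How reasonable that is depends on whether power for 0.9 is 0.93 or 0.79.
- **Completion.** With two possible targets, stopping at 40 could be reported either as completion or as missing the target by a third.

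**Working it through.** **Inputs**

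- Total N = 60 (Participants).
- Allocation 1:1, so 30 per arm. This is inferred from the Timeline section, which enters one participant per group at a time.
- Effect size 0.9, alpha 0.05, beta 0.19 (Participants).
- Test: the group-by-session interaction (Analyses). With two groups and two sessions it is equivalent to a two-sample t-test on change scores.
- Assumptions not in the documents: a two-sided test, and 0.9 as the between-group difference in units of the change-score SD.

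**Formulas, n per arm**

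- Normal approximation: power = Φ(0.9·√(n/2) − 1.96).
- Exact: noncentral t with 2n − 2 degrees of freedom and noncentrality 0.9·√(n/2).

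**Attempt to reproduce 0.81 at N = 60**

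- 0.9·√15 = 3.486, and 3.486 − 1.960 = 1.526, so the normal approximation gives 0.9365.
- The exact t calculation gives 0.929.
- Beta is therefore about 0.07, against the stated 0.19.

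**Size at which 0.81 holds**

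| Total N | Per arm | Normal | Exact t |
|---|---|---|---|
| 40 | 20 | 0.812 | 0.792 |
| 42 | 21 | 0.831 | 0.812 |
| 50 | 25 | 0.889 | 0.877 |
| 60 | 30 | 0.9365 | 0.929 |

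Solving the normal formula for power 0.81 gives 20 per arm, 40 in total. In the other direction, the effect detectable with power 0.81 (exact t) is 0.745 at N = 60 and 0.921 at N = 40.

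**Other readings tried at N = 60**

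- One-sided test: 0.964 (t), further from 0.81.
- Rank test with efficiency 0.955 or 0.864: 0.917 or 0.888.
- Attrition of 10%, 20% or 30%: 0.901, 0.863 or 0.812. About 30% loss is needed.
- Reduced alpha: 0.814 at alpha 0.0125, but both the Participants and Analyses sections give 0.05.
- Unequal allocation: 0.806 at 13:47, contrary to one participant per group in the Timeline section.
- Effect in raw-score SDs with pre-post correlation ρ. The change-score effect is then 0.9/√(2(1 − ρ)). Power is 0.68 at ρ = 0, 0.77 at ρ = 0.2, 0.83 at ρ = 0.3 and 0.93 at ρ = 0.5. It equals 0.81 at ρ ≈ 0.27, where the change-score effect is 0.9/√1.46 = 0.745.

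**Accrual**

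- 20 months × 2 per month = 40, and 40/60 = 67% of the stated enrolment.
- 2 + 20 + 2 = 24 months in all, so no other testing time is scheduled.
- Sixty participants need 60/20 = 3 per month, or 60/2 = 30 months at the stated rate.

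**The case against.** The strongest reply is that 0.93 is conditional. The plan names neither the sidedness nor the SD behind 0.9. If 0.9 is in raw-score SDs, a pre-post correlation of about 0.27 gives 0.81 at 60, and that is not an extraordinary value. This stands as a qualification: 0.81 cannot be recovered from the inputs stated, but one unstated input would recover it. It does not help the schedule. On that reading the 40 participants in the timeline would have power of only about 0.63.

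Second, the 60 may be those recruited and the 40 those tested and trained. Enrolment happens at consent, dropout is foreseen, and participants whose research scans show more than minimal white matter disease are to be excluded. But no loss rate is given, moving from 60 to 40 takes a 33% loss, and the power sentence is attached to the 60. People who leave after testing begins would also use up places in the schedule.

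Third, if 60 are enrolled, the stated power is too low on the reading used here, which is a conservative error. Nothing in it biases the effect estimate or raises the type I error. In addition, the Analyses section uses a Bayes factor, computed from the data, to separate a true null from low power, so the planning figure does not decide that question. Both points are fair and limit the harm to interpretation. They leave the accrual gap untouched.

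Finally, the match at 40 is exact only for the normal approximation; the t calculation reaches 0.81 at 42. That 60 replaced a smaller target without the other figures being updated is a plausible inference, but the documents do not say so.

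**Conclusion.** The concern holds. Under 1:1 allocation, a two-sided alpha of 0.05 and 0.9 as a standardised difference on the change score, 60 participants give power 0.93, about 12 percentage points above the stated 0.81. The stated power fits 40 to 42 participants. Independently of any statistical assumption, the timeline provides for 40 participants, 20 fewer than the stated enrolment. The routes that would bring power at 60 down to 0.81 are either absent from the documents or contradicted by them, and none makes the schedule deliver 60 tested participants. The three figures cannot all be right as written.

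**What to change.** Decide which size governs, then make the Participants and Timeline sections agree.

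- **Define the effect size.** State what 0.9 is standardised by, the sidedness and the test. If it is in raw-score SDs, give the assumed pre-post correlation and recompute power from it.
- **If 60 is the target.** On the change-score reading, state that 30 per group gives power 0.93 for an effect of 0.9, or 0.81 for an effect of about 0.75, at two-sided alpha 0.05. Change the timeline to 3 participants per month for 20 months, or 2 per month for 30 months.
- **If 40 is the target.** Change 60 to 40 and state power as 0.79 (exact t).
- **If 60 is meant to allow for losses.** State the assumed loss rate, and the number expected to complete, on which power is then based.

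The restatement costs some wording and one recalculated figure, and needs no participants beyond the 60 already stated. Keeping 60 does carry a practical cost: testing must run 50% faster, or the project grows from 24 to 34 months (2 + 30 + 2). The documents give no capacity figure that supports the faster rate, so the sponsor should confirm that it is achievable.

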Study flow (Fig. 2): Participants will take part in an initial session of behavioral testing and fMRI scanning, and another similar session after training. In the intervening 3 weeks, they will attend 12 training sessions of one hour each, comprising either the experimental or control intervention. These sessions will take place each weekday from Monday-Thursday, beginning the Monday after the initial session, and will be conducted via the internet with the participant at home, using CVNR-issued iPads. The Friday of each week will be used for repeat testing on the spatial imagery task to assess the extent of improvement as a result of the preceding four days' training. This design allows 12 hours of training over 3 weeks, comparable to that used in prior studies of spatial cognitive training (Wright et al., 2008; Terlecki et al., 2008). In addition, it allows us to

assess weekly improvement, thus providing crucial data for design of a larger study in the future. Importantly, CVNR investigators have experience using iPads with their built-in accessibility for those with visual impairments, and experience with this kind of telehealth application. They have found that even older, technologically naïve caregivers (mean age 78±4.1) can learn to use novel technologies such as the iPad; with a high degree of reported satisfaction (Griffiths et al., 2016). Specifically, Co-investigator [name] has expertise in use of telehealth technology with visually impaired participants in a VA project where he assessed the accessibility of smart phones including the iPhone and in an NIH SBIR project in which the accessible and award-winning MoneyReader app was developed for the iPhone and iPad. The training sessions will employ a haptic grid overlay on the iPad screen during training, and

software will be developed to enable remote communications and viewing of the subject's movements and finger position on the screen of the iPad.

Spatial imagery task: The imagined grid used for the spatial imagery task as well as for spatial cognitive training will be a 5x5 grid using the numbers 1-25, with 1-5 on the first row from left to right, 6-10 on the second row from left to right, and so on (**Fig. 3**). Participants will first

Initial positions: white numbers. Arrows: shortest paths from initial to final position, intersecting with mentally traced sequence (right) or not (left).

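### Covariates are to be chosen from the imbalances observed, with no list or threshold; a short list including the baseline score should be fixed in advance

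*Combined protocol and SAP*

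**What the plan says.** Under Research Design and Methods, PARTICIPANTS, the plan states: "We will recruit 60 blind participants, randomized by our CVNR statistician into two groups". It gives no allocation ratio, block size, stratification factor or minimisation. It continues: "The randomization process should result in a balance between the intervention and control groups with respect to a range of variables". The list that follows is open. It names age, sex, age of onset, duration of visual loss, duration of loss of light perception, and comorbid conditions. The remedy for imbalance is that "any residual differences will be accounted for as covariates in statistical analyses".

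The ANALYSES section specifies, for each behavioural measure, a repeated-measures ANOVA with group and session as factors, and "the null hypothesis will be rejected in case the interaction is significant at" the 0.05 level. It names no covariate for that test. Later in the same section, baseline behavioural and imaging measures are to be tried as predictors of change. That is a separate question about individual differences and does not adjust the comparison between arms.

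**The concern.** Some difference between arms will exist on every variable, so the rule cannot be carried out until someone decides what counts as a difference. The plan leaves that decision until the data are in hand. It selects covariates by the size of the imbalance, not by how strongly they predict the outcome.

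Two further gaps force a choice. Current age is essentially age of onset plus duration of visual loss, so these three cannot all enter one linear model. In addition, a covariate measured once per person changes the group-by-session test only if its interaction with session is also fitted, and the plan does not say whether it will be.

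The trial's stated purpose, at the end of Preliminary Studies, includes supplying an effect size for planning a larger trial. An estimate that depends on a covariate choice made after the data are seen is a weaker basis for that. Meanwhile the baseline score, which is collected on everyone, enters the main test only through the change from it.

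**Working it through.** **Inputs.** The PARTICIPANTS section gives N = 60, six named variables, effect size 0.9 and alpha 0.05. I assume equal arms, a two-sided test, and 0.9 as a standardised mean difference. The documents give no R² and no pre-post correlation, so those below are assumptions.

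**1. The plan's own figure.** The plan says "this sample size has a power of 0.81 to detect an effect size of 0.9 with" alpha 0.05. The two-sided t-test gives power 0.929 at 30 per arm (0.937 by the normal approximation), so 0.81 is not reproduced. At 20 per arm it is 0.792 (0.812 normal). The TIMELINE says "Next 20 months: Test and train 2 subjects per month, one in each group", which gives 2 × 20 = 40 participants. That mismatch is a separate matter, but it is why both arm sizes are shown here.

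**2. Chance imbalance.** The standardised difference in one variable is about Normal with SD √(2/n).

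- 30 per arm: 0.5/√(2/30) = 1.94, so P = 0.053. At least one of six: 1 − (1 − 0.053)⁶ = 0.28.
- 20 per arm: 0.5/√(2/20) = 1.58, so P = 0.114. At least one of six: 1 − (1 − 0.114)⁶ = 0.52.
- Because age, onset and duration are linearly dependent, at most five variables are free: 1 − (1 − 0.053)⁵ = 0.24 and 1 − (1 − 0.114)⁵ = 0.45.

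Sex is binary and comorbidity is not a single normal variable, so these figures are approximate.

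**3. False-positive rate.** These are simulations with no true effect and a nominal rate of 5%. They used seven covariates (one more than the six named), assumed R² 0.2 to 0.5, and 20 or 30 per arm. A run with six covariates showed the same pattern.

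| Covariate rule | False-positive rate |
|---|---|
| No adjustment, or a fixed list | 4.8% to 5.1% |
| One rule: imbalance p<0.05 | about 4% to 4.6% (individual runs 3.8% to 4.8%) |
| One rule: imbalance p<0.10 | 2.9% to 3.9% |
| Best result among four p-value thresholds | 5.5% to 7.3% |
| Same, plus single imbalanced covariates | 7.5% to 9.3% |
| Best of none, p<0.05, p<0.10, difference >0.25 SD | 8.9% to 9.9% |

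**4. Power at effect 0.9.** This compares the p<0.05 imbalance rule with three covariates fixed in advance, drawn from a list of this type, where R² is the share explained by all seven.

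| Per arm | R² | Imbalance rule | Three fixed | Gain (points) |
|---|---|---|---|---|
| 30 | 0.2 | 93.1% | 93.5% | 0.4 |
| 30 | 0.4 | 93.6% | 95.9% | 2.3 |
| 20 | 0.2 | 77.6% | 79.5% | 1.9 |
| 20 | 0.4 | 79.5% | 84.3% | 4.8 |

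**5. Baseline score.** With two sessions, the group-by-session test is a comparison of change, whose variance is 2σ²(1 − ρ). ANCOVA on the post-training score has residual variance σ²(1 − ρ²). The ratio is (1 + ρ)/2, or 0.75 at an assumed ρ of 0.5. If 0.9 is in units of the SD of change, it becomes 0.9/√0.75 = 1.04.

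- 20 per arm: noncentrality 1.039/√[(2/20)(1 + 1/36)] = 3.24 on 37 df, so power is 0.88 against 0.79 for change.
- 30 per arm: 1.039/√[(2/30)(1 + 1/56)] = 3.99 on 57 df, so power is 0.975 against 0.929.

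**The case against.** The strongest case on the other side has four parts.

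- **Randomisation.** The plan says balance should result, not that it will, and silence about the method does not show that simple randomisation is used. A reader might infer that balance is left wholly to chance and therefore not delivered. The documents do not support that: the text says only "randomized by our CVNR statistician into two groups", and the TIMELINE's pairing hints at some restriction, though on numbers and not on prognosis. This part stands. The most that can be said is that balance is not assured.
- **Restricted eligibility.** Enrolment is limited to people over 50 who lost light perception within five years, expressly to reduce heterogeneity, and neurological and cognitive impairment are excluded. This makes a given imbalance smaller in years. It does not change the chance of a gap of 0.5 SD, because the SD shrinks too.
- **Baseline already used.** The ANOVA includes the pre-training score, and baseline measures are also tried as predictors. This is partly right, but change is not adjustment for baseline, and the predictor analysis is not the arm comparison.
- **False positives.** A reader might infer that the plan inflates the error rate. It does so only if several rules are tried and the best result reported. The wording permits this but does not plan it, and a single rule applied mechanically errs the other way.

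The trial is also a feasibility and effect-size study, which lowers the stakes of any one test but not the need for a stable estimate.

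**Conclusion.** The concern holds in a limited form. The adjustment rule is stated, selects on observed imbalance, and has no list, threshold or model form, so the adjusted result depends on choices made after the data are seen. At least one imbalance of 0.5 SD or more has a chance of about 28% (30 per arm) or 52% (20 per arm) under independence, and somewhat less given the linked variables. The false-positive rate is about 4% to 4.6% under one mechanical p<0.05 rule. It is about 6% to 9% if rules are chosen after seeing results, depending on the menu, and slightly higher in the least favourable setting.

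A reader might go further and infer that the test is biased, or that the plan gives up a large amount of power. Neither follows. Chance imbalance does not bias a randomised comparison. A gap as wide as 79% against 90% appears only at 20 per arm with R² 0.4 and all seven covariates adjusted, which is not the short list proposed here. For three covariates of the listed type the gain is about 0 to 3 points at 30 per arm and up to about 5 at 20 per arm. It is larger for the baseline score if the pre-post correlation is moderate. All power gains rest on assumed prognostic strength.

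**What to change.** Replace the sentence on residual differences with a covariate list fixed before the first randomisation: the baseline value of the outcome being analysed, age, and duration of visual loss. Fit every behavioural between-arm analysis as an ANCOVA of the post-training score on arm and these three covariates, whatever imbalance is seen, and make the ANALYSES section say the same. Report other baseline differences descriptively, without testing them and without adding them to the model. Age of onset is then redundant, which removes the linear dependence.

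The cost is protocol wording and three residual degrees of freedom (58 to 55 at 30 per arm, 38 to 35 at 20 per arm). The list should stay short. Seven covariates of no prognostic value would lower power from 0.929 to 0.893 at 30 per arm and from 0.792 to 0.699 at 20 per arm.

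Stratifying on baseline imagery accuracy is optional and not part of the required change. The documents supply no cut-point, and allocation would have to wait for a score acquired during the first scan, with training "beginning the Monday after the initial session". One sentence stating the allocation method would remove the doubt about how balance is sought.
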